9.1. Exposure

DEFINITY® will be administered as a diluted bolus injection. 1.3 mL of activated DEFINITY® will be diluted with 8.7 mL of preservative-free saline to evenly distribute microspheres. An initial injection of up to 3 mL of diluted DEFINITY® will be administered with subsequent injections of 1 to 2 mL, as needed. Information about the administration of DEFINITY® is collected on the case report form. Exposure to DEFINITY® study drug will be summarized. The number and percentage of ITT subjects who are administered DEFINITY® will be presented. Summary statistics of the dose administered (mL) will be summarized for the safety population.

9.2. Treatment Compliance

Not applicable

9.3. Adverse Events

A treatment-emergent adverse event (TEAE) is an AE that started or worsened in severity following the start of administration of DEFINITY®. A table of AEs will be summarized for the following:

- Number of subjects having experienced at least one TEAE
- Number of subjects having experienced at least one TEAE related to DEFINITY®
- Number of subjects having experienced at least one TEAE related to study procedure
- Number of subjects having experienced at least one severe TEAE
- Number of subjects with study procedure interrupted due to a TEAE
- Number of subjects with study procedure interrupted due to a TEAE related to DEFINITY®
- Number of subjects with study procedure interrupted due to a TEAE related to the study procedure
- Number of subjects having experienced at least one serious TEAE
- Number of subjects having experienced at least one serious TEAE related to DEFINITY®
- Number of subjects having experienced at least one serious TEAE related to a study procedure
- Number of subjects having experienced at least one severe serious TEAE
- Number of subjects with study procedure interrupted due to a serious TEAE
- Number of subjects with study procedure interrupted due to a serious TEAE related to DEFINITY®
- Number of subjects with study procedure interrupted due to a serious TEAE related to the study procedure
- Number of subjects having experienced a fatal TEAE
- Number of subjects having experienced a fatal TEAE related to DEFINITY®
- Number of subjects having experienced a fatal TEAE related to the study procedure

If an AE is described as being 'related to DEFINITY®', unless otherwise stated, this will be defined as a relationship to DEFINITY® administration where the relationship is defined as either possibly related or related. If an AE is described as being 'related to study procedure', unless otherwise stated, this will be defined as a relationship to DEFINITY® enhanced echo and/or DEFINITY® administration and/or unenhanced echo and/or CMR where the relationship is defined as either possibly related or related.

This document is confidential.

A summary table of TEAEs (number and percentage of subjects who experienced an AE and number of events) grouped by primary SOC and PT will be presented for the following categories of events:

- All TEAEs
- All TEAEs related to DEFINITY®
- All TEAEs related to study procedure
- All serious TEAEs
- All serious TEAEs related to DEFINITY®
- All serious TEAEs related to study procedure
- All severe TEAEs
- All TEAEs leading to study discontinuation

A summary table of TEAEs by SOC and PT will also be presented by maximum severity.

A subject with more than one occurrence of the same AE in a particular SOC and PT will be counted only once in the total of subjects experiencing AEs in that particular SOC and PT, respectively. If a subject experiences the same AE at more than one severity, or with more than one relationship category, the most severe rating or the stronger causal relationship will be reported.

Any missing severity or relationship of an AE should be replaced by the worst case as follows:

- If severity is missing, then the AE will be included in the “severe” category
- If relationship is missing, then the AE will be included as “related to DEFINITY®”

Time to onset and duration of events in days will also be listed where:

- Time to onset is defined as (AE start date – date of DEFINITY® administration)
- Duration of event is defined as (AE stop date – AE start date + 1)

AEs with missing start dates will be included in the count of events, but a time will not be calculated. AEs will be coded using MedDRA version 21.0 or higher.

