6.8 Echocardiography Imaging Procedures

6.8.1 Image Acquisition

A bedside resting transthoracic echocardiogram will be performed by personnel trained in study procedures according to standardized instructions provided here and in the study Imaging Manual. Unenhanced echocardiography will be performed in each of the standard A2C, A3C, and A4C views after optimization of these views. At least 3 consecutive cardiac cycles should be recorded in standard digital format in each view. After unenhanced imaging has been conducted, study drug will be administered as described above and in the Dose Preparation and Administration Guide. DEFINITY®-enhanced images will be obtained with low or very low MI imaging using a standardized and harmonized method consistent with practice guidelines. After study drug administration and subsequent image optimization, the same A2C, A3C, and A4C views should be obtained as with unenhanced imaging over at least 3 consecutive cardiac cycles.

Subjects will remain at the site for observation until at least 30 minutes after the end of the administration of study drug.

All images will then be transferred to an Imaging Core Laboratory for further analysis. No site analysis will be performed. Instructions for echo data transfer and storage at the central imaging laboratory will be provided in the study Imaging Manual.

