6.10 Adverse Event Assessments

6.10.1 Performing Adverse Event Assessments

In this clinical trial, an AE is defined as any new untoward medical occurrence or worsening in severity or frequency of a pre-existing medical condition in a study patient, which does not necessarily have a causal relationship with investigational product. AEs occurring from the

time the informed consent is signed until the 72±24 hour telephone follow-up will be reported. Treatment-emergent adverse events (TEAEs) are a safety endpoint and are discussed in Section 8.4.1. The NCI-CTCAE version 4.0 will be utilized for Adverse Event (AE) reporting of severity by grade.

An AE can, therefore, be any unfavorable and unintended sign (including an abnormal laboratory finding, for example), symptom or disease temporally associated with the use of a medicinal (investigational or marketed) product, whether or not considered related to the medicinal (investigational or marketed) product.

Note: For this clinical trial, observations and findings (previously unknown) discovered during the procedures and medically assessed as most-likely pre-existing (e.g., myocardial wall hypokinesis, thrombus, cardiac valve deficits, and so on) will not be considered AEs and will not be reported as such in the eCRF. However, these observations and any hospitalizations/treatments required to treat the new findings will be reported elsewhere in the eCRF. Any complications resulting from the study procedures (e.g., intravenous extravasations) *will* be recorded as an AE.

A medication error is defined as any event related to the administration of a medicinal or investigational product that may cause or lead to inappropriate use or patient harm. Medication errors can be actual or potential errors and may include misuse, administration error, overdose, under-dose, or abuse. For this clinical trial, any medication errors (e.g., administration error, overdose, etc., that occur at the time of study product administration) must be recorded as an AE.

All identified AEs must be recorded and described on the appropriate AE section of the eCRF by the investigator (or designee). If known, a diagnosis should be recorded, rather than multiple individual symptoms. In addition to the event term, the following information should be captured for all AEs:

- Date (and time) of onset and resolution
- Severity of the event (see definitions below)

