8.4 Safety Endpoint(s)

8.4.1 Primary Safety Endpoint(s)

Safety analyses will include tabulations of the incidence (number and percent of subjects) of treatment-emergent adverse events (TEAEs) and procedure-related AEs by MedDRA system organ class (SOC) and preferred term (PT). This will be repeated for serious adverse events, for adverse events leading to study withdrawal and for adverse events at least possibly related to study procedures. This will be performed on the safety population.

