3.3. Brief Description

This is a Phase 3, prospective, open-label, multicenter study to evaluate LVEF measurement accuracy and reproducibility of DEFINITY® contrast-enhanced and unenhanced echocardiography as compared with non-contrast cardiac magnetic resonance imaging (CMR) used as the truth standard. Approximately one-hundred fifty (150) subjects will be enrolled over approximately 10 months at approximately 10 centers located in the United States. The study population will consist of male and female subjects 18 years of age of older.

Subjects will be screened based on LVEF measurements obtained via 2D echo with or without contrast or other methods (e.g. CMR, MUGA scan) obtained within 6 months of enrollment (Day 0). Subjects will be stratified to achieve an approximately even distribution within four pre-defined LVEF groups (>50, 41-50, 30-40, <30%). LVEF for screening purposes will be determined by the investigator and based on measurements with 2D echo or other methods (e.g. CMR, MUGA scan) obtained within 6 months prior to enrollment (Day 0). The site investigator will determine whether an echocardiogram is optimal or sub-optimal based on the unenhanced echocardiogram performed on Day 0. Subjects with optimal and sub-optimal echocardiograms (based on investigator opinion) will be enrolled. An echocardiogram is considered sub-optimal if 2 or more segments of the ventricular border are classified as not adequately visualized.

Each subject will undergo an unenhanced ultrasound examination and a DEFINITY® contrast-enhanced examination on the same day at Day 0. A minimum of 360 seconds of images will be collected during both the unenhanced and the DEFINITY® contrast-enhanced examinations. Subjects will remain at the clinical site for at least 30 minutes of observation after DEFINITY® administration. A safety follow-up

This document is confidential.

phone call will be conducted for all subjects at approximately 72 ± 24 hours after completion of the imaging sessions, including DEFINITY® administration.

Enrolled subjects will be followed for adverse events (AEs), serious adverse events (SAEs), and changes in concomitant medications from the time the Informed Consent is signed through the safety follow-up telephone call.

A non-contrast CMR will be used as the truth standard. CMR studies will be performed within ±30 days of the echocardiographic assessments at Day 0. Final assignment of each subject to an LVEF group will be determined by CMR.

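### SAP 9.3 counts unenhanced echo and CMR as study procedures but tabulates only treatment-emergent events, and AE follow-up appears to close before most of the permitted post-dose CMR days

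*SAP*

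**What the plan says.** **Definition and tables.** SAP 9.3 treats an event as procedure-related if it is linked to the enhanced echo, the DEFINITY injection, or "unenhanced echo and/or CMR where the relationship is defined as either possibly related or related". The same section states: "A treatment-emergent adverse event (TEAE) is an AE that started or worsened in severity following the start of administration of DEFINITY". Every row of the overview and every SOC/PT table that follows is a TEAE summary. The procedure-related SOC/PT table is headed "All TEAEs related to study procedure".

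**What the protocol planned.** Protocol 8.4.1 plans the incidence of "treatment-emergent adverse events (TEAEs) and procedure-related AEs by MedDRA system organ class" and preferred term, then repeats this for, among others, events at least possibly related to study procedures. SAP 11.1 says that nothing has changed from the protocol's analyses.

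**Order of procedures.** Protocol 6.8.1: "After unenhanced imaging has been conducted, study drug will be administered". For the reference scan, SAP 3.3 says: "CMR studies will be performed within ±30 days of the echocardiographic assessments at Day 0".

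**Follow-up.** Protocol 6.10.1 has AEs occurring from the "time the informed consent is signed until the 72±24 hour telephone follow-up will be reported". The protocol synopsis, protocol 3.3 and 6.10.2, and SAP 4.3 time the end of follow-up from DEFINITY. Protocol Appendix 1 times both the call and the CMR from the echo session. Protocol 3.1 and SAP 3.3 and 3.8.3 instead place the call after completion of the imaging sessions, in the plural.

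**The concern.** There are two gaps of different kinds.

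The first is in tabulation. The unenhanced echo always precedes DEFINITY, and the CMR may. An event that begins during either, before the injection, is not treatment-emergent unless it later worsens. The SAP includes these procedures in its definition and then applies a filter that removes their pre-dose events. That is narrower than protocol 8.4.1, and the narrowing is not declared.

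The second is in collection. If follow-up ends with a call two to four days after dosing, an event at a CMR done later lies outside the follow-up period, although that CMR is required by the protocol and supplies the truth standard for the subject.

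A reader of the clinical study report would take the procedure-related rows as evidence on all four components of the definition. A zero for unenhanced echo or CMR could reflect the filter and the window and not an absence of events.

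**Working it through.** **Step 1. Which events reach a summary table.** Inputs: the TEAE definition and procedure list (SAP 9.3), the order of imaging (protocol 6.8.1), the CMR window (SAP 3.3 and 3.8.4), the AE window (protocol 6.10.1, SAP 4.3) and the missing-date rule (SAP 6.2.3). Follow-up is taken to close 72±24 hours after DEFINITY.

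| Event | Recorded? | In a SAP 9.3 summary? |
|---|---|---|
| Unenhanced echo; onset before injection, no later worsening | Yes | No |
| Unenhanced echo; onset or worsening after injection | Yes | Yes |
| CMR after consent but before dosing; onset before injection, no later worsening | Yes | No |
| Same CMR; onset or worsening after injection, up to the call | Yes | Yes |
| Start date incomplete and order relative to DEFINITY undeterminable | Yes | Yes, dated to the DEFINITY day |
| CMR between dosing and the call; onset before the call | Yes | Yes |
| CMR after the call | Outside stated follow-up | No, unless reported anyway |

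The rows with a recorded event and no summary are the tabulation gap. They need no assumption about scan dates.

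**Step 2. The plan's own figure.** Protocol 3.3 gives a maximum participation of 41 days. As a sum of windows, 7 (screening) + 30 (CMR) + 4 (72+24 h) = 41, so the figure reproduces. If the call is timed from DEFINITY, the windows overlap and the span is shorter: Day −7 to Day +30 is 37 days, and Day −30 to Day +4 is 34 days. A sum of 41 fits a call made up to four days after a Day +30 CMR, but it also fits a simple addition of the three windows. It does not settle the anchor.

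**Step 3. Permitted post-dose CMR days after closure.** The call at 72±24 h falls on Day 2, 3 or 4. Days left = 30 − call day.

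- Day 2: 30 − 2 = 28; 28/30 = 93%
- Day 3: 30 − 3 = 27; 27/30 = 90%
- Day 4: 30 − 4 = 26; 26/30 = 87%

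**Step 4. Days on which a CMR-related event is, as a rule, both collected and tabulated.** Day 0 (after dosing) up to the call is 3 to 5 days of the 61 permitted: 3/61 = 5% to 5/61 = 8%.

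**Step 5. Shares of scans, on assumption only.** The documents give no distribution of CMR dates. Two even spreads show the range:

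| Assumed spread | Before Day 0 | Day 0 to the call | After the call |
|---|---|---|---|
| Day −30 to +30 (61 days) | 30/61 = 49% | 5% to 8% | 26/61 to 28/61 = 43% to 46% |
| Day −7 to +30 (38 days) | 7/38 = 18% | 3/38 to 5/38 = 8% to 13% | 26/38 to 28/38 = 68% to 74% |

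The second spread corresponds to CMR only after consent within the 7-day screening window. A CMR earlier than that may precede consent as standard of care, when AE collection has not yet begun by design.

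**The case against.** The best defence has five parts.

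1. *TEAE status depends on time of onset, not cause.* This stands. A reader might infer that events from the unenhanced echo or an earlier CMR can never be TEAEs. The documents do not support that: an event attributed to either that starts or worsens after the injection counts, and so does one whose start date cannot be placed before dosing.

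2. *The call may follow the CMR.* Protocol 3.1 and SAP 3.3 and 3.8.3 refer to imaging sessions, Appendix 1 gives the CMR its own imaging session, and 41 days would fit. This stands as an inconsistency. More passages anchor to DEFINITY, and Appendix 1 times the CMR from the echo session, so closure on Day 2 to 4 is the better-supported reading, but it is not settled.

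3. *Reporting duties exist without a cutoff.* Protocol 6.10.1 requires complications of study procedures to be recorded as AEs. Protocol 6.10.6.1 requires reporting of serious events that result from the investigational procedure, and 6.10.6.2 requires all SAEs within one calendar day. A reader might infer that a serious event at a late CMR would certainly go unreported. These passages do not allow that. However, the synopsis, protocol 3.1 and SAP 4.3 do set a window for SAEs, so an investigator has conflicting instructions.

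4. *Pre-dose events are not lost.* This stands for consented subjects: they are recorded, and subject listings are planned. What is missing is the summary.

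5. *TEAE summaries are usual for a drug safety question, and few events are expected.* This is fair. The CMR is non-contrast, and subjects with known CMR contraindications or claustrophobia are excluded. It does not explain why the SAP includes CMR and unenhanced echo in the definition, or why it departs from protocol 8.4.1 without saying so.

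**Conclusion.** The point holds in two parts.

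**Tabulation.** SAP 9.3 leaves out of every summary table those procedure-related events that begin before dosing and do not worsen. This rests only on the SAP's definitions and on the plain reading of protocol 8.4.1, in which treatment-emergent qualifies the first item and not the procedure-related AEs. The narrowing is undeclared.

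**Collection.** If follow-up ends 72±24 hours after DEFINITY or the echo session, as most passages say, 26 to 28 of the 30 permitted post-dose CMR days lie beyond it. The passages on the call's anchor and on reporting duties do not agree, so this is a conflict to resolve and not a proven exclusion.

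A reader might also infer that most CMR exposure goes unmonitored. The documents do not support that, because they count permitted days and say nothing about when scans took place. The 43% to 74% of scans after the call in the working rests on assumed even timing.

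The practical effect is on how the procedure-related rows can be read. The DEFINITY-related safety tables and all efficacy analyses are unaffected.

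**What to change.** 1. In SAP 9.3, beside the TEAE tables, add a table of all procedure-related AEs from consent, whatever their onset relative to DEFINITY, by SOC and PT and split by procedure (unenhanced echo, DEFINITY administration, enhanced echo, CMR). This restores what protocol 8.4.1 lists. If the TEAE restriction is kept instead, declare it in SAP 11.1.

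2. Reconcile the passages on the call's anchor (synopsis, protocol 3.1, 3.3, 6.10.2 and Appendix 1; SAP 3.3, 3.8.3 and 4.3), and the AE/SAE window with the CMR window, so that events at a CMR after the call are recorded.

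3. SAP section 2 describes this SAP as commissioned following enrollment, so step 2 may come too late. In that case keep CMR in the definition and footnote the tables: CMR-related events were systematically collected only up to the safety call. A statement that CMR events were not collected would be untrue, because those between consent and the call are, and removing CMR from the definition would discard recorded attributions.

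The cost is one extra table and, if the windows are aligned, one AE question at a visit that already takes place.

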9.4. Laboratory Evaluations

A urine pregnancy test will be performed at screening and Day 0 as applicable. Results will be listed.

9.5. Vital Signs

The vital sign measurements are collected only at the screening/baseline visit. The following vitals will be summarized at baseline using descriptive statistics: systolic/diastolic blood pressure (BP), heart rate, and respiratory rate. In addition, all vital signs will be listed by subject.

This document is confidential.

The number and percentage of subjects with potentially clinically significant vital sign values at baseline will be tabulated. Potentially clinically significant vital sign values are detailed below and should be used to determine what is 'normal' and 'potentially clinically significant':

Parameter	Unit	Normal Range	Potentially Clinically Significant
Heart Rate	Beats per minute	60 – 100	1) <50 bpm 2) >100 bpm
Systolic BP	mmHg	90 – 139	1) >190 mmHg 2) <80 mmHg
Diastolic BP	mmHg	60 – 89	1) >110 mmHg 2) <50 mmHg

9.6. Physical Examination

Physical examination body system inspection results are collected at baseline and will be listed.

9.7. Study Center Effects

The mean "absolute value of the difference versus CMR" for each of DEFINITY[®], and unenhanced echocardiography, as well as the difference between the two treatments with respect to this mean, will be presented for each study center and each blinded reader. Within each blinded reader, an assessment of study center effect on the mean treatment difference will be assessed using a one-way ANOVA. For each blinded reader, a site difference that is not significant at the 0.15 level of significance, or a site difference that is significant but where for every site the mean treatment difference is more favorable for DEFINITY[®] than unenhanced echocardiography, will support pooling subjects across sites for the primary analysis for that reader.

This document is confidential.

10. Interim Analyses

This study will utilize an adaptive design that allows one interim sample size re-calculation after a minimum of 75 subjects have been enrolled and followed. The pre-specified maximum allowable adjusted sample size following re-estimation will be 300 enrolled, or two times the initial planned sample size of 150 enrolled. The re-estimation of sample size will be conducted by an independent, unblinded biostatistician following a pre-specified plan using the method Mehta and Pocock (2011). Specifically, at the interim stage, the conditional power (CP) for obtaining a significant beneficial effect of DEFINITY® over unenhanced imaging with respect to the primary endpoint will be calculated for each blinded reader, using the protocol-specified planned sample size of 150 enrolled subjects (approximately 143 evaluable subjects assuming 5% premature withdrawal). This conditional power will be calculated under the assumption that the interim estimate of the mean unenhanced-DEFINITY® difference in LVEF accuracy is the true population mean difference. Specifically, the calculation of conditional power and sample size increase will be as follows:

Let μ_D be the true mean of the absolute value of the differences between the DEFINITY®-enhanced echo LVEF and the CMR LVEF, and let μ_U be the true mean of the absolute value of the differences between the unenhanced echo LVEF and the CMR LVEF. After a minimum of 75 subjects are enrolled and followed (which should lead to approximately 71 evaluable subjects), an unblinded interim analysis will be conducted to determine whether sample size should be increased to maintain adequate conditional power of up to 90% for each reader. Conditional Power (CP) for rejecting the null hypothesis in favor of DEFINITY® by the planned final sample size of 143 evaluable subjects is calculated as follows for each reader:

$$CP = P \left(Z > \frac{c_2 \sqrt{I_2} - t_1 \sqrt{I_1} - (I_2 - I_1)\Delta}{\sqrt{I_2 - I_1}} \right)$$

where,

- a. Z is a random standard normal variate
- b. c_2 is the t -critical value to be used in the final analysis = 1.97681 (one-sided 0.025 level of significance; with 142 degrees of freedom assuming the final evaluable sample size is 143, which is the number of evaluable subjects expected for the final analysis with 150 enrolled subjects with 5% premature withdrawal).
- c. Δ is the assumption of the true difference “ μ_U minus μ_D ” where μ_D is the mean of the absolute value of the differences between the DEFINITY®-enhanced echo LVEF and the CMR LVEF, and μ_U is the mean of the absolute value of the differences between the unenhanced echo LVEF and the CMR LVEF; Δ will be set to the interim sample's point estimate of μ_U minus μ_D ; i.e., Δ will be set to $\bar{x}_U - \bar{x}_D$, where \bar{x}_U and \bar{x}_D are the sample mean point estimates of μ_U and μ_D , respectively.
- d. I_1 is the observed “information” at the interim analysis; specifically, $I_1 = \frac{1}{s^2/n_1}$ where s = the interim sample point estimate of the standard deviation of the difference between the unenhanced and DEFINITY® echo's “absolute value of the difference versus CMR” and n_1 is the interim sample size.
- e. I_2 is the anticipated “information” at the final analysis; specifically, $I_2 = \frac{1}{s^2/n_2}$ where s is as defined in item 'd' directly above and n_2 is the planned final evaluable sample size = 143.
- f. t_1 is the interim paired t -statistic testing the null hypothesis, derived from the interim sample point estimates of the mean and standard deviation of the difference between the unenhanced and DEFINITY® echo's “absolute value of the difference versus CMR”.

This document is confidential.

The study will not be stopped for overwhelming efficacy or futility at this interim stage. Instead, based on Table 1 of Mehta and Pocock (2011), the following algorithm will be carried out:

- If the CP $\leq 36\%$ for at least two of the three blinded readers based on the final sample size, the study will continue to its original planned sample size of 150 enrolled subjects.
- If the CP $\geq 90\%$ for at least two of the three blinded readers based on the final sample size, the study will continue to its original planned sample size of 150 enrolled subjects.
- If $36\% < CP < 90\%$ for exactly two out of the three readers, let n be the total protocol-specified enrolled sample size. Assume n_a is the total enrolled sample size for reader 1 to reach 90% CP, n_b is the total enrolled sample size for reader 2 to reach 90% CP, and n_c is the total enrolled sample size for reader 3 to reach 90% CP. Without loss of generality, assume both reader 1 and 2 had a CP within the range of $36\% < CP < 90\%$, reader 3 did not. Using this example, the final total number of enrolled subjects will be the sample size with which both readers have more than 90% CP but not exceeding $2n$; i.e., $\min(\max(n_a, n_b), 2n)$. All 3 readers' final analysis will be based on this $\min(\max(n_a, n_b), 2n)$ enrolled subjects.
- If $36\% < CP < 90\%$ for all three readers, the final total number of enrolled subjects will be the sample size with which all readers have more than 90% CP but not exceeding $2n$; i.e., $\min(\max(n_a, n_b, n_c), 2n)$. Each reader's final analysis will be based on $\min(\max(n_a, n_b, n_c), 2n)$ enrolled subjects.

The number of enrolled subjects is not changed from the final protocol-specified sample size in any other cases. That is, in all such other cases, each reader's final analysis will be based on the n enrolled subjects.

The sample size may be increased up to 300 enrolled subjects (twice the protocol-planned sample size) for a given reader in order to obtain 90% CP. As stated above, if different sample size increases are specified for different readers, only the largest sample size increase will be shared with those blinded to the results. Thus, all readers will review the same number of scans and each reader's final analysis will be based on the number of subjects enrolled in the study.

The statisticians, sponsor, and investigators will remain blinded to the interim results for the duration of the ongoing study. After the interim analysis is carried out, the recommendation made to the sponsor will be either to keep sample size as is or to increase enrolled sample size to a given value not greater than 300. No other information derived from this interim analysis, including the reason for the recommendation, will be provided to the sponsor and other blinded personnel.

This document is confidential.

11. Changes from Planned Analysis

